## 7.1.2. Recording and Reporting of Adverse Events

For recording of adverse events, the study period is defined for each patient as the time period from signature of the ICF to the end of the final study period. The final period of recording of adverse events is defined as 24 weeks after the first dose of IMP (visit 8). The period for reporting treatment-emergent adverse events is defined as the period after the first dose of IMP is administered and until the end of the final study period (visit 8).

All adverse events that occur during the defined study period must be recorded both on the source documentation and the CRF, regardless of the severity of the event or judged relationship to the test IMP. For serious adverse events and protocol-defined adverse events of special interest, the serious adverse event form must be completed and the serious adverse event or the adverse event of special interest must be reported immediately (Section 7.1.5.3.1). The investigator does not need to actively monitor patients for adverse events once the study has ended. Serious adverse events and adverse events of special interest occurring after the defined study period should be reported to the sponsor if the investigator becomes aware of them, following the procedures described in Section 7.1.5.3.1.

At each contact with the patient, the investigator or designee must question the patient about adverse events by asking an open-ended question such as "Have you had any unusual symptoms or medical problems since the last visit? If yes, please describe." All reported or observed signs and symptoms will be recorded individually, except when considered manifestations of a medical condition or disease state. A precise diagnosis will be recorded whenever possible. When such a diagnosis is made, all related signs, symptoms, and any test findings will be recorded collectively as a single diagnosis on the CRF and, if it is a serious adverse event, on the serious adverse event form.

The clinical course of each adverse event will be monitored at suitable intervals until resolved, stabilized, or returned to baseline; or until the patient is referred for continued care to a healthcare professional; or until a determination of a cause unrelated to the test IMP or study procedure is made.

The onset and end dates, duration (in case of adverse event duration of less than 24 hours), action taken regarding IMP, treatment administered, and outcome for each adverse event must be recorded both on the source documentation and the CRF.

The severity, seriousness, and relationship of each adverse event to the test IMP and study procedures, as judged by the investigator, must be recorded as described below.

Further details are given in the Safety Monitoring Plan.

## 7.1.3. Severity of an Adverse Event

The severity of each adverse event must be recorded as one of the following:

**Mild:** No limitation of usual activities

**Moderate:** Some limitation of usual activities

**Severe:** Inability to carry out usual activities

For severity grading of local tolerability (ie, injection site erythema, injection site induration, injection site ecchymosis, and injection site pain), please refer to Section 7.9.

# 7.1.4. Relationship of an Adverse Event to the Test Investigational Medicinal Product

The relationship of an adverse event to the test IMP is characterized as follows:

Table 3: The Relationship of an Adverse Event to the Test IMP

Term	Definition	Clarification
No reasonable possibility (not related)	This category applies to adverse events that, after careful consideration, are clearly due to extraneous causes (disease, environment, etc) or to adverse events that, after careful medical consideration at the time they are evaluated, are judged to be unrelated to the investigational medicinal product (IMP).	
 
The relationship of an adverse event may be considered "no reasonable possibility" if it is clearly due to extraneous causes or if at least 2 of the following apply:
 
It does not follow a reasonable temporal sequence from the administration of the IMP.
 
It could readily have been produced by the patient's clinical state, environmental or toxic factors, or other modes of therapy administered to the patient.
 
It does not follow a known pattern of response to the IMP.
 
It does not reappear or worsen when the IMP is re-administered.
 

Reasonable possibility (related)	This category applies to adverse events for which, after careful medical consideration at the time they are evaluated, a connection with the administration of IMP cannot be ruled out with certainty.	
 
The relationship of an adverse event may be considered "reasonable possibility" if at least 2 of the following apply:
 
It follows a reasonable temporal sequence from administration of the IMP.
 
It cannot be reasonably explained by the known characteristics of the patient's clinical state, environmental or toxic factors, or other modes of therapy administered to the patient.
 
It disappears or decreases on cessation or reduction in dose. There are important exceptions when an adverse event does not disappear after discontinuation of the IMP, yet an IMP relationship clearly exists.
 
It follows a known pattern of response to the IMP.
 

#### 7.1.5. Serious Adverse Events

For recording of serious adverse events, the study period is defined for each patient as the time period from signature of the ICF to the end of the study period. Serious adverse events occurring in a patient after the end of the study period should be reported to the sponsor if the investigator becomes aware of them, following the procedures described in Section 7.1.5.3.1.

#### 7.1.5.1. Definition of a Serious Adverse Event

A serious adverse event is an adverse event occurring at any dose that results in any of the following outcomes or actions:

- results in death
- is life-threatening adverse event (ie, the patient was at risk of death at the time of the event); it does not refer to an event which hypothetically might have caused death if it were more severe

- requires inpatient hospitalization or prolongation of existing hospitalization, which
  means that hospital inpatient admission or prolongation of hospital stay were required
  for treatment of an adverse event, or that they occurred as a consequence of the event
  Hospitalizations scheduled before the patient signed the ICF will not be considered
  serious adverse events, unless there was worsening of the preexisting condition
  during the patient's participation in this study.
- results in persistent or significant disability/incapacity (refers to a substantial disruption of one's ability to conduct normal life functions)
- is a congenital anomaly/birth defect
- an important medical event that may not result in death, be life-threatening, or require hospitalization but may jeopardize the patient and may require medical intervention to prevent one of the outcomes listed in this definition

Examples of such events are intensive treatment in an emergency room or at home for allergic bronchospasm, blood dyscrasias or convulsions that do not result in hospitalization, or the development of drug dependency or drug abuse. Note: Any suspected transmission of an infectious agent via a medicinal product is considered an important medical event.

All occurrences of possible drug-induced liver injury that meet Hy's law criteria, defined as all of the below, must be reported by the investigator to the sponsor as a serious adverse event:

- alanine aminotransferase (ALT) or aspartate aminotransferase (AST) increase of >3× the upper limit of normal (ULN)
- total bilirubin increase of >2× ULN
- absence of initial findings of cholestasis (ie, no substantial increase of alkaline phosphatase)
- no other explanation for the observed abnormalities

An adverse event that does not meet any of the criteria for seriousness listed above will be regarded as a nonserious adverse event.

#### 7.1.5.2. Expectedness

A serious adverse event that is not included in the Adverse Reaction section of the relevant reference safety information (RSI) by its specificity, severity, outcome, or frequency is considered an unexpected adverse event. The RSI for this study is the IB.

The sponsor's GPSP will determine the expectedness for all serious adverse events.

For the purpose of SUSAR reporting, the version of the IB at the time of occurrence of the SUSAR applies.

## 7.1.5.3. Reporting a Serious Adverse Event

## 7.1.5.3.1. Investigator Responsibility

To satisfy regulatory requirements, all serious adverse events that occur during the study, regardless of judged relationship to administration of the test IMP, must be reported to the sponsor by the investigator. The event must be reported within 24 hours of when the investigator learns about it. Completing the serious adverse event form and reporting the event must not be delayed, even if not all the information is available. The investigator does not need to actively monitor patients for adverse events once this study has ended.

Serious adverse events occurring to a patient after the last administration of IMP of that patient has ended but before the final study visit (visit 8) should be reported to the sponsor if the investigator becomes aware of them.

The serious adverse event form should be sent to the local safety officer (LSO) or designee (a contract research organization [CRO] in a country without a sponsor LSO) (contact information is in the Clinical Study Personnel Contact Information section); the LSO will forward the report to the sponsor's GPSP.

The following information should be provided to record the event accurately and completely:

- study number
- investigator and investigational center identification number
- patient number
- onset date and detailed description of adverse event
- investigator's assessment of the relationship of the adverse event to the test IMP (no reasonable possibility, reasonable possibility)

#### Additional information includes:

- age and sex of patient
- date of first dose of IMP
- date and amount of last administered dose of IMP
- action taken
- outcome, if known
- severity
- explanation of assessment of relatedness
- relevant concomitant medication (including doses, routes of administration, and regimens) and treatment of the event
- pertinent laboratory or other diagnostic test data
- relevant medical history
- results of dechallenge/rechallenge, if known

- for an adverse event resulting in death
  - cause of death (whether or not the death was related to test IMP)
  - autopsy findings (if available)
  - autopsy report if autopsy was done

Each report of a serious adverse event will be reviewed and evaluated by the investigator and the sponsor to assess the nature of the event and the relationship of the event to the test IMP, study procedures, and to underlying disease.

Additional information (follow-up) about any serious adverse event unavailable at the initial reporting should be forwarded by the investigator within 24 hours of when it becomes known to the same address as the initial report.

The sponsor's GPSP will distribute the Council for International Organizations of Medical Sciences form/Extensible Markup Language file to the LSO/CRO for submission to the competent authorities, Independent Ethics Committee (IEC)/Institutional Review Board (IRB), and investigators, according to regulations. The investigator must ensure that the IEC/IRB is also informed of the event, in accordance with national and local regulations.

For double-blind studies, blinding will be maintained for all study personnel. Therefore, in case of a SUSAR, only the LSO/CRO will receive the unblinded report for regulatory submission; the others will receive a blinded report.

Note: Although pregnancy is not a serious adverse event, the process for reporting a pregnancy is the same as that for reporting a serious adverse event but using the pregnancy form (see Section 7.2).

#### 7.1.5.3.2. Sponsor Responsibility

If a serious unexpected adverse event is believed to be related to the test IMP or study procedures, the sponsor will take appropriate steps to notify all investigators participating in the sponsored clinical studies of fremanezumab and the appropriate competent authorities (and IEC/IRB, as appropriate).

In addition to notifying the investigators and competent authorities (and IEC/IRB, as appropriate), other action may be required, including the following:

- altering existing research by modifying the protocol
- discontinuing or suspending the study
- modifying the existing consent form and informing all study participants of new findings
- modifying listings of expected toxicities to include adverse events newly identified as related to fremanezumab

#### 7.1.6. Protocol-Defined Adverse Events Not for Expedited Reporting

Not applicable.

### 7.1.7. Protocol-Defined Adverse Events of Special Interest

For purposes of this protocol, the following are considered protocol-defined adverse events of special interest to be sent to the sponsor's GPSP for evaluation: ophthalmic-related adverse events of at least moderate severity, events of possible drug-induced liver injury (AST or ALT ≥3× ULN, total bilirubin ≥2× ULN, or international normalized ratio >1.5), Hy's Law events, or events of anaphylaxis and severe hypersensitivity. Refer to Appendix I for guidance regarding monitoring of patients with elevated liver function tests. Anaphylaxis and severe hypersensitivity will be monitored using the diagnostic criteria for anaphylaxis as outlined by the 2006 Joint National Institute of Allergy and Infectious Disease/Food Allergy and Anaphylaxis Network Second Symposium on Anaphylaxis (Sampson et al 2006) (see Appendix J). In the event of expected anaphylaxis and severe hypersensitivity, vital signs, including oxygen saturation and respiration rate, will be measured. Other assessments will be performed at the discretion of the investigator.

The process for reporting a protocol-defined adverse event of special interest is the same as that for reporting a serious adverse event (Section 7.1.5.3). These adverse events of special interest to be reported to GPSP can be either serious or nonserious, according to the criteria outlined in Section 7.1.5.1.

#### 7.1.8. Protocol Deviations Because of an Adverse Event

If a patient experiences an adverse event or medical emergency, deviations from the protocol may be allowed on a case-by-case basis. To ensure patient safety, after the event has stabilized or treatment has been administered (or both), the investigator or other physician in attendance must contact the physician identified in the Clinical Study Personnel Contact Information section of this protocol as soon as possible to discuss the situation. The investigator, in consultation with the sponsor, will decide whether the patient should continue to participate in the study.

# 7.2. Pregnancy

Any female patient becoming pregnant during the study will discontinue IMP. All pregnancies of women participating in the study and female partners of men participating in the study that occur during the study or within at least 40 weeks after administration of the first dose of the IMP are to be reported immediately to the individual identified in the Clinical Study Personnel Contact Information section of this protocol, and the investigator must provide the sponsor (LSO/CRO) with the completed pregnancy form. The process for reporting a pregnancy is the same as that for reporting a serious adverse event but using the pregnancy form (Section 7.1.5.3).

The investigator is not required to report patients who are found to be pregnant between screening and baseline, provided no protocol-related procedures were applied.

All female patients or female partners of men participating in the study who become pregnant will be monitored for the outcome of the pregnancy (including spontaneous, elective, or voluntary abortion). Female partners of men participating in the study who become pregnant will be asked to sign an ICF. If the pregnancy continues to term, the outcome (health of the infant up to 8 weeks of age), including details of birth and presence or absence of any birth defect, congenital abnormalities, or maternal and newborn complications, will be reported to the sponsor. Any complication of pregnancy during the study and any complication of pregnancy

that the investigator becomes aware of after withdrawal from the study will be reported as an adverse event or serious adverse event, as appropriate.

If the pregnancy in the woman participating in the study and/or the female partners of men participating in the study does not continue to term, one of the following actions will be taken:

- For a spontaneous abortion, report as a serious adverse event.
- For an elective abortion due to developmental anomalies, report as a serious adverse event.
- For an elective abortion **not** due to developmental anomalies, report on the pregnancy form; do not report as an adverse event.

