The pharmacokinetics (non-compartmental analysis) of fremanezumab demonstrated an increase in  $C_{max}$  and AUCs values slightly greater than dose proportionality over sc dose range of 225 to 900 mg. Median time to maximum observed concentration ( $t_{max}$ ) values generally occurred 5 to 7 days post sc doses. Mean values for apparent volume of distribution ( $V_z/F$ ) after a single sc dose ranged from 5.7 to 6.4 L at 225 mg to 900 mg sc doses. The mean apparent total body clearance (CL/F) ranged from 0.0777 to 0.0895 mL/min at this dose range. The mean  $t_{1/2}$  ranged from 32.2 to 36.2 days. Fremanezumab exposure parameters and overall pharmacokinetic profile was similar for healthy Japanese and Caucasian subjects. Comparison of exposure parameters ( $C_{max}$  and  $AUC_{0-\infty}$ ) from Study LBR-101-011 and TV48125-PK-10078 at the 225 and 900 mg sc dose levels indicates a 2.9 to 3.5 fold higher exposure in Study TV48125-PK-10078 relative to LBR-101-011 study. The main reason for the difference in exposure appears to be the bioanalytical method used in the plasma sample analysis.

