- i. Women may be included only if they have a negative serum beta-human chorionic gonadotropin (β-HCG) test at screening and a negative urine pregnancy test at baseline, are sterile, or postmenopausal. Definitions of sterile and postmenopausal are given in Appendix D.
- j. Women of childbearing potential (WOCBP) whose male partners are potentially fertile (ie, no vasectomy) must use highly effective birth control methods for the duration of the study (ie, starting at screening) and for 30 weeks after the last IMP administration. Further details are included in Appendix D.
- k. Men must be sterile or, if they are potentially fertile or reproductively competent (ie, not surgically or congenitally sterile) and their female partners are of childbearing potential, must use, together with their female partners, a condom for the duration of the study and for 30 weeks after the last IMP administration. Further details are included in Appendix D.
  - l. Definitions of WOCBP, sterile and postmenopausal women, male contraception, and highly effective birth control methods, including examples, are given in Appendix D.

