#### **5.1.1.1.** Starting Dose and Dose Levels

Patients randomized to fremanezumab will receive 675 mg of fremanezumab administered as 3 sc injections (225 mg/1.5 mL each) at visit 2 (randomization), visit 3 (week 4), and visit 4 (week 8). Patients will then enter the open-label period of the study, where they will receive

675 mg of fremanezumab administered as 3 sc injections (225 mg/1.5 mL each) at visit 5 (week 12), visit 6 (week 16), and visit 7 (week 20).

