#### 5.5.2. Blood Donation

Patients may not donate blood while taking the IMP and for 5 half-lives (7.5 months) after the last dose of IMP.

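### The minimum window for reporting pregnancies (40 weeks from the first dose) ends up to 10 weeks before the required contraception period (30 weeks from the last dose) in patients given open-label doses

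*Protocol*

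**What the plan says.** Section 7.2 covers pregnancies in female patients and in the female partners of male patients. It requires immediate notification of those that "occur during the study or within at least 40 weeks after administration of the first dose of the IMP are to be reported immediately".

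Section 4.1 sets the contraception period from the other end of treatment. Criterion j requires women of childbearing potential with potentially fertile partners to use highly effective methods "for the duration of the study (ie, starting at screening) and for 30 weeks after the last IMP administration". Criterion k requires men whose partners are of childbearing potential to use "a condom for the duration of the study and for 30 weeks after the last IMP administration".

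Dosing under Section 5.1.1.1 is at weeks 0, 4 and 8 (double-blind), then at weeks 12, 16 and 20 (open-label). Section 3.1 sends all patients straight into the open-label phase at visit 5. Visit 8, at week 24, is the last visit and the end of adverse event recording (Sections 3.1 and 7.1.2).

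**The concern.** Contraception is required because the sponsor wants to avoid conception while exposure may persist. Pregnancy reporting is the matching safeguard for when contraception fails, so it should last at least as long. Here one period is counted from the first dose and the other from the last, and each added dose lengthens only the second.

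The words "occur during the study or within at least 40 weeks after administration of the first dose of the IMP are to be reported immediately" set a floor. A site may report later pregnancies, but it has no duty to notify one that begins after week 40. The limb about pregnancies during the study does not help, because the study ends at week 24.

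What may be lost is early notice to the sponsor of an otherwise uncomplicated pregnancy, and with it a prospective start to outcome follow-up. The people affected are women of childbearing potential and such partners of male patients. Sample size, type I error and power are untouched.

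**Working it through.** The 40 weeks is a stated rule, so there is no figure to reproduce. The check is calendar arithmetic.

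**Inputs**
- Reporting minimum: week 40 after the first dose (Section 7.2).
- Contraception: 30 weeks after the last dose (Section 4.1, j and k).
- Dosing weeks: 0, 4, 8, 12, 16, 20 (Section 5.1.1.1), with a visit tolerance of ±3 days (Table 1).

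**Formula:** end of contraception = week of last dose + 30; shortfall = that week − 40.

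| Last dose (week) | Contraception ends (week) | Shortfall (weeks) | With ±3 days on the last dose |
|---|---|---|---|
| 0 | 30 | none | none |
| 4 | 34 | none | none |
| 8 | 38 | none | none |
| 12 | 42 | 2 | 1.6 to 2.4 |
| 16 | 46 | 6 | 5.6 to 6.4 |
| 20 | 50 | 10 | 9.6 to 10.4 |

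The 40-week minimum covers 40 − 8 = 32 weeks after a week-8 dose, but only 40 − 20 = 20 weeks after a week-20 dose. Placebo counts as IMP (Section 5.1), so a patient randomized to placebo starts the clock at a placebo injection. Counted from that patient's first fremanezumab dose at week 12, the minimum covers 40 − 12 = 28 weeks.

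**Exposure in the uncovered weeks.** This assumes simple exponential decline after a week-20 dose. Section 1.2.2.1 gives mean half-lives that "ranged from 32.2 to 36.2 days". Section 5.5.2 bars blood donation "for 5 half-lives (7.5 months) after the last dose of IMP", which implies 7.5/5 = 1.5 months per half-life; I take this as about 45 days.

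| Half-life (days) | Half-lives by week 40 (140 days) | Remaining at week 40 | Remaining at week 50 (210 days) |
|---|---|---|---|
| 32.2 | 4.35 | 4.9% | 1.1% |
| 36.2 | 3.87 | 6.9% | 1.8% |
| 45 (assumed) | 3.11 | 11.6% | 3.9% |

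The blood-donation limit also runs from the last dose. At 7.5 months, or 32.6 weeks, it reaches week 20 + 32.6 = 52.6.

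**The case against.** The strongest reply accepts the arithmetic and disputes its weight.

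- **Few people are affected.** Amendment 01 added the open-label period. The Amendment History shows 70 patients enrolled at that date and 87 at Amendment 02, so 87 − 70 = 17 enrolled in between. Those who had already finished under the earlier schedule had a last dose at week 8 and no gap. This stands: 87 is a true ceiling but a loose one. The number of the 70 still in double-blind treatment is not given.
- **Other provisions cover the consequence.** Section 7.2 says that female patients and partners "who become pregnant will be monitored for the outcome of the pregnancy", with no time limit. It also treats spontaneous abortion, and elective abortion for developmental anomalies, as serious adverse events. Section 7.1.2 adds that post-study serious adverse events and events of special interest "should be reported to the sponsor if the investigator becomes aware of them". This stands in part. Section 7.1.5.3.1 states that pregnancy is not itself a serious adverse event, and Section 7.1.7 does not list it as of special interest. The sponsor cannot oversee follow-up of a pregnancy it has not been told about.
- **The benchmark is a choice.** Nothing in the protocol says the two periods must match. Five half-lives at 32.2 to 36.2 days is 23.0 to 25.9 weeks. On that measure the shortfall is about 3 to 6 weeks after a week-20 dose, 0 to 2 after week 16 and none after week 12. But the half-life implied by Section 5.5.2 removes this reduction, and 30 weeks is the period the sponsor itself chose.
- **The risk is low.** Section 1.2.1 reports no apparent embryo-fetal toxicity in rabbits and no treatment-related effect on embryo-fetal survival or development in rats. This bears on urgency but does not change the contraception rule.
- **The practical yield is small.** Weeks 40 to 50 fall 16 to 26 weeks after visit 8, so detection depends on patients contacting the site. True, but weeks 24 to 40 already work that way.

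**Conclusion.** The concern holds. For patients dosed in the open-label period, the reporting minimum stops 2, 6 or 10 weeks before required contraception ends, according to whether the last dose is at week 12, 16 or 20. No other section extends it. Patients whose last dose is at week 8 or earlier are fully covered.

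The likely cause is that the 40 weeks was not revisited when Amendment 01 added three doses and removed the follow-up visit at about week 40 (Section 16.6). That is an inference.

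The conclusion assumes that the sponsor's own contraception period is the right yardstick for pregnancy notification. The gap falls in the low-exposure tail and concerns first notice of uncomplicated pregnancies, in a number of people the documents do not give. It is a worthwhile safety-reporting correction and not a critical defect.

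**What to change.** Reword the window in Section 7.2 to cover pregnancies occurring during the study, or within at least 30 weeks after the last dose of IMP or 40 weeks after the first dose, whichever is later. This covers the contraception period in Section 4.1 (j and k) for every patient. Keeping the 40-week limb means that nobody who stops early has a shorter window than now.

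The cost is one sentence, by amendment or letter of clarification; the sponsor has already issued nine such letters for this study. No visits or procedures are added. Sites carry the reporting duty for up to 10 weeks longer. Because these weeks fall after visit 8, patients would need to be told, at or before that visit, to contact the site if a pregnancy occurs. The new window would still end before the blood-donation restriction, at week 50 against about week 53 after a full course.
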